|-------------------------------------|--|-------------------------------------|-----------------------|
| Name of company | | Tabulated Trial Protocol | |
| Boehringer Ingelheim | | | |
| Name of finished product: | | | |
| Not applicable | | | |
| Name of active ingredient: | | | |
| BI 836909 | | | |
| Protocol date: | Trial number: | | Revision date: |
| 10 Feb 2015 | 1351.1 | | 26 Nov 2018 |
| Number of patients | | | |
| total entered: | Up to 50 patients depending on dose level reached | | |
| Each treatment: | Dose escalation: | | |
| | Number of patients will depend on the number of dose levels to be tested before MTD determination or determination of the recommended dose. Based on preclinical data, it is expected that > 5 dose levels in addition to the 4 single-patient doses will be tested. Up to 50 patients will be treated during the dose escalation phase. Up to 6 additional patients will be treated with MTD or recommended dose. | | |
| Diagnosis : | Patients with relapsed and/or refractory multiple myeloma | | |
| Main criteria for inclusion: | 
Patients with relapsed and/or refractory multiple myeloma and progression after ≥ 2 prior treatment lines (including proteasome inhibitor and immunomodulatory drugs).
 
Patients with significant comorbidities such as impaired renal function, cardiovascular diseases (i.e. uncontrolled hypertension, unstable angina, history of infarction within past 6 months, congestive heart failure > NYHA II), active infection requiring treatment, or active autoimmune disease will be excluded.
 | | |
| Test product(s): | BI 836909 in vials for continuous intra-venous infusion | | |
| Comparator products: | N/A | | |
| Duration of treatment: | 
Treatment will continue for up to 5 cycles or until:
 
 • Disease progression or start of further anticancer treatment • Non-acceptable toxicity • Patient decision to withdraw consent • Investigator's decision 
In case of ongoing clinical benefit after five courses additional 5 courses may be given if considered indicated by the treating investigator.
 | | |

Proprietary confidential information.

© 2018 Boehringer Ingelheim International GmbH or one or more of its affiliated companies. All rights reserved.

This document may not - in full or in part - be passed on, reproduced, published or otherwise used without prior written permission.

| | | | |

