For the dose levels 0.2 to 1.6 µg/day single patient cohorts are entered since no clinical activity is expected at these doses.

If a patient has been on treatment in one of the above-mentioned dose cohorts for 2 weeks without DLT the first patient of the next higher dose cohort will be entered if agreed on by the safety committee. If a patient has reached DLT, then the safety committee recommends the switch to a 3 + 3 cohort for the dose level at which the DLT occurred. Patients may not proceed to the next higher dose level before completion of 6 patients.

One intra-patient dose escalation is allowed within the single patient dose cohorts if the initial dose is tolerated well and no DLT occurs during 1st cycle. In case of DLT additional patients will be entered into this cohort following a 3+3 design.

For the dose levels ≥ 3.2 µg/day 3-6 patients will be treated per dose level and observed for 4 weeks during the first cycle before decision for dose escalation to the next dose cohort is made.

Per dose level 1 patient will be enrolled and treated for 1 week, then further patients will be enrolled. Patients should be entered sequentially. Additional patients should not start treatment before the previous patient has been treated for 48 hours in order to monitor initial transient toxicities due to cytokine release syndrome.

In the dose escalation part the trial safety committee (for details see [Section 3.1.1](#)) can determine to enter additional and intermediate dose cohorts at any time e.g. if DLTs or other safety events, pharmacodynamics activity or antitumor efficacy occur. The safety committee will also determine to switch from single patient cohorts to a 3+3 design at doses below **3.2µg/d** if DLTs, pharmacodynamic activity or antitumor efficacy occur.

PK/PD data might be taken into account for dose escalation decisions if available.

Patients should be entered sequentially. Treatment initiation of more than 1 new patient per day will not be permitted during the dose escalation phase.

Once the MTD or the recommended dose for better characterization of safety and early evaluation of anti-tumour activity is determined up to 6 additional patients will be treated with MTD or the recommended dose.

Proprietary confidential information.

© 2018 Boehringer Ingelheim International GmbH or one or more of its affiliated companies. All rights reserved.

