5.2.3 Adverse event collection and reporting

AE Collection

The following must be collected and documented on the appropriate eCRF by the Investigator:

- From signing the informed consent onwards through the Residual Effect period (REP) which is 30 day after EOT until the end of REP all AEs (serious and non-serious) and AESIs must be reported
- After the end of REP until trial completion all related SAEs and related AESIs must be reported.

The REP is defined as 30 days after the last administration of study medication. All AEs which occurred through the treatment phase and throughout the REP will be considered as on treatment please. Events which occurred after the REP will be considered as post treatment events.

After the last per protocol contact the Investigator does not need to actively monitor patients for AEs. However, if the Investigator becomes aware of SAEs or AESIs that occurred after the last per protocol contact, the SAEs and AESIs should be reported by the Investigator to the Sponsor if considered relevant by the investigator.

Patients may be hospitalized during selected phases of the study as required per protocol, e.g., monitoring of trial drug administration, collection of blood for pharmacokinetic purposes, or for administrative reasons. Hospitalizations for administrative reasons and other hospitalizations already planned at the screening visit need not be reported as a SAE in case they are performed "as planned".

Proprietary confidential information.

© 2018 Boehringer Ingelheim International GmbH or one or more of its affiliated companies. All rights reserved.

This document may not - in full or in part - be passed on, reproduced, published or otherwise used without prior written permission.

The investigator must report the following events via telephone/fax using the SAE form immediately (within 24 hours) to the sponsor: SAEs and non-serious AEs occurring at the same time as an SAE and/or which are medically related to the SAE(s), and Protocol-specified adverse event of special interest. With receipt of any further information to these events, a follow-up SAE report has to be provided. SAEs and non-serious AEs must include a causal relationship assessment made by the investigator.

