7.3.4 Safety analyses

Adverse events will be coded using the Medical Dictionary for Regulatory Activities (MedDRA) coding dictionary. Standard BI summary tables and listings will be produced. Statistical analysis and reporting of adverse events will concentrate on treatment-emergent adverse events. To this end, all adverse events occurring between start of treatment and end of the residual effect period (“REP”; see definition in [Section 5.2.3](#)) will be considered ‘treatment-emergent’. Adverse events that start before first drug intake and deteriorate under treatment will also be considered as ‘treatment-emergent’.

Key measures of safety will include:

- The incidence and intensity (according to CTCAE criteria version 4.03) of adverse events;
- Time course and distribution of patients by maximum CTCAE grade according to version 4.03;
- Time course of laboratory changes

The severity and timing of adverse events will indicate the tolerability of the treatment regimen. Adverse events will be evaluated using the CTCAE grading scheme version 4.03. The overall incidence and intensity of adverse events, as well as relatedness of adverse events to treatment with BI 836909 will be reported for all dose cohorts. Serious adverse events will be tabulated. In addition, events leading to dose reduction or treatment discontinuation will be examined, but may not be reported as individual tables, depending upon the extent of overlap with the occurrence of DLT.

Laboratory data will be analysed both quantitatively as well as qualitatively. The latter will be done via comparison of laboratory data to their reference ranges. Values outside the reference range as well as values defined as clinically relevant will be highlighted in the listings.

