6. GENERAL ANALYSIS DEFINITIONS

6.1 TREATMENTS

Patients are administered BI 836909 as a continuous 4-week infusion followed by a 2-week break for 5 cycles or until progression, unacceptable adverse events or other reason necessitating withdrawal. In case of ongoing clinical benefit a maximum of 5 additional treatment cycles can be given.

[figure not shown]

Figure 6.1:1 Overall study design

For all analyses, statistics will be tabulated by treatment dose group (see [Table 6.1: 1](#)).

Table 6.1: 1 Treatment labels for use in the CTR

Treatment label	Short label
BI 836909, 0.2 µg/d, c.i.v. ^[1]	0.2 µg/d civ
BI 836909, 0.4 µg/d, c.i.v. ^[1]	0.4 µg/d civ
BI 836909, 0.8 µg/d, c.i.v. ^[1]	0.8 µg/d civ
BI 836909, 1.6 µg/d, c.i.v. ^[1]	1.6 µg/d civ
BI 836909, 3.2 µg/d, c.i.v.	3.2 µg/d civ
BI 836909, 6.5 µg/d, c.i.v.	6.5 µg/d civ
BI 836909, 13 µg/d, c.i.v.	13 µg/d civ
BI 836909, 25 µg/d, c.i.v.	25 µg/d civ
BI 836909, 50 µg/d, c.i.v.	50 µg/d civ
BI 836909, 100 µg/d, c.i.v.	100 µg/d civ
BI 836909, 200 µg/d, c.i.v.	200 µg/d civ
BI 836909, 400 µg/d, c.i.v.	400 µg/d civ
BI 836909, 800 µg/d, c.i.v. ^[2]	800 µg/d civ

[1] The 1st four treatment label (0.2 – 1.6 µg/d) may be combined into one column for selected displays.

[2] Further doses will be tested in case that MTD could not be confirmed at a dose level of 800 µg/day. Intermediate doses cohorts will be entered if determined by the safety committee, for example, in case that the dose cohort 400 µg/day exceeds MTD (>1 patients out of 6 with DLT) and no DLT is observed on 200 µg/day, 300 µg/day might be considered.

The purpose of the definition below is to describe the different study interval in this trial.

The treatment periods of the study are:

- Screening period:
The screening period starts from the date of informed consent and ends at the date of the first administration of study drug.
- Treatment period:

Treatment period starts from the date of the first administration of study drug and ends at the date of the last administration of study drug.

- Residual effect period:

Residual effect period starts from the date of the last administration of study drug + 1, and ends at the date of the last administration of study drug + 30 days .

- Follow-up period;

The Follow-up period starts from the last administration of study drug + 30 days.

Please see [Table 6.1:2](#) below, for a definition of treatment periods. The purpose of the definitions below is to describe the treatment periods in this trial.

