7. PLANNED ANALYSIS

For all the analyses in this open label phase I trial, patients will be included in the dose cohorts they were originally assigned to.

Tabulations of frequencies for categorical data will include all possible categories and will display the number of observations in a category as well as the percentage (%) relative to the respective treatment group. The category “missing” will be displayed where applicable (i.e., if and only if there are actually missing values in the data).

For in-text tables, the set of summary statistics is: N (number of patients with non-missing values), mean, standard deviation (SD), median, Q1 (lower quartile), Q3 (upper quartile), depending on the data.

For end-of-text tables, the set of summary statistics is: N/Mean/SD/Q1/Median/Q3. For appendix tables, the set of summary statistics is: N/Mean/SD/Min/Q1/Median/Q3/Max.

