7.8.1 Adverse events

Unless otherwise specified, the analyses of adverse events will be descriptive in nature. All analyses of AEs will be based on the number of subjects with AEs and NOT on the number of AEs.

For analysis multiple AE occurrence data on the CRF will be collapsed into an AE provided that all of the following applies:

- All AE attributes are identical (LLT, intensity, action taken, therapy required, seriousness, reason for seriousness, relationship, outcome, AE of special interest)
- The occurrences were time-overlapping or time-adjacent (time-adjacency of 2 occurrences is given if the second occurrence started on the same day or on the day after the end of the first occurrence).

For further details on summarization of AE data, please refer to [\[3, 4\]](#).

The analysis of adverse events will be based on the concept of treatment emergent adverse events. That means that all adverse events occurring between first drug intake till last drug intake + residual effect period will be assigned to the treatment. All adverse events occurring before first drug intake will be assigned to 'screening' and all adverse events occurring after the residual effect period will be assigned to 'post-treatment' (for listings only). For details on the treatment definition, see [Section 6.1](#).

According to ICH E3 [\[5\]](#), AEs classified as 'other significant' needs to be reported and will include those non-serious adverse events leading to treatment discontinuation or non-serious AEs leading to dose reduction.

An overall summary of adverse events will be presented. This summary will include the first 6 categories from the list below and AEs by highest intensity graded according to CTCAE (version 4.03).

The frequency of subjects with adverse events will be summarised by treatment, primary system organ class and preferred term (mention MedDRA levels to be displayed in the tables).

Separate tables will be provided for patients with each of the following AE categories:

- All AEs,
- DLTs (Course 1 only¹),
- DLTs (All courses),
- AEs leading to dose reduction,

- AEs leading to treatment discontinuation,
- Serious AEs,
- Drug related AEs,
- Drug related serious AEs,
- CTCAE Grade 3 or higher AEs,
- AEs leading to death,

[1]: Course 1 defined by from start of treatment to start of Cycle 2 or the last dose administration of BI 836909 during Cycle 1 + 30 days, whichever occurs earlier.

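### Apart from DLTs, AE tables compare dose groups over unequal times on drug, and the SAP as provided lists no AE time course

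*SAP*

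**What the plan says.** - **Counting unit.** SAP 7.8.1: "All analyses of AEs will be based on the number of subjects with AEs and NOT on the number of AEs".
- **Counting window.** The same section says that "all adverse events occurring between first drug intake till last drug intake + residual effect period will be assigned to the treatment". Protocol 5.2.3 fixes the tail: "The REP is defined as 30 days after the last administration of study medication". The window therefore lengthens with each further course.
- **Grouping.** SAP 6.1: "For all analyses, statistics will be tabulated by treatment dose group". SAP 7 adds that "patients will be included in the dose cohorts they were originally assigned to". Later changes of dose within a patient do not move that patient's events to another column.
- **Course 1 output.** In SAP 7.8.1 DLTs have a table limited to Course 1, with the window defined in footnote 1. All AEs, drug-related AEs, SAEs, grade 3 or higher AEs and AESIs have all-course tables only.
- **Time on drug.** Treatment stops at progression, unacceptable toxicity, withdrawal of consent or by investigator decision. The protocol synopsis adds: "In case of ongoing clinical benefit after five courses additional 5 courses may be given if considered indicated by the treating investigator". Protocol 4.1.1 gives a maximum of 10 cycles. For the four lowest doses, protocol 3.1 says that "single patient cohorts are entered since no clinical activity is expected at these doses".
- **Timing of AEs.** Protocol 7.3.4 lists among its key measures of safety "Time course and distribution of patients by maximum CTCAE grade according to version 4.03". SAP 7.8.1 lists a summary by highest intensity but no AE output with a time axis.
- **Exposure.** SAP 7.7 summarises treatment days and cycles by dose group, separately from the AE tables.

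**The concern.** A percentage of patients with an event depends on how long they were watched as well as on the risk per unit of time. Here the length of observation is an outcome of treatment. Patients who benefit stay on and patients who progress or do not tolerate the drug leave, and both may vary with dose. Two dose columns can therefore differ because of dose, because of exposure, or both.

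What is at stake is the description of the safety profile and the choice of a recommended dose, both secondary objectives. Protocol 2.2 makes the recommended dose depend partly on safety data if the MTD is not reached. Protocol 5.2.1.1 excludes most haematological AEs and several grade 3 events (fever, hypotension and fatigue among them) from the DLT definition, yet says that haematological AEs will be weighed when the dose for further development is defined. Those events appear only in the all-course tables. Protocol 3.1 also anticipates early, transient toxicity from cytokine release, which an all-course percentage mixes with events arising months later.

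**Working it through.** **Inputs from the documents.** A course is 42 days, 28 on infusion and 14 off (flow chart, note 1). The residual effect period is 30 days (protocol 5.2.3). The maximum is 5 + 5 = 10 courses, which reproduces the figure in protocol 4.1.1. There is no AE rate and no power calculation to reproduce.

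**Assumption.** The same AE risk *p* per course at every dose and in every course, shown for 5% to 30%.

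**1. Length of the counting window after *k* full courses:** 42(*k* − 1) + 28 + 30 days.
- *k* = 1: 58 days
- *k* = 5: 168 + 58 = 226 days
- *k* = 10: 378 + 58 = 436 days, which is 436/58 = 7.5 times the one-course window

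**2. Expected percentage of patients with an event after *k* courses:** 1 − (1 − *p*)^*k*.

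| *p* per course | 1 course | 5 courses | 10 courses |
|---|---|---|---|
| 5% | 5% | 23% | 40% |
| 10% | 10% | 41% | 65% |
| 20% | 20% | 67% | 89% |
| 30% | 30% | 83% | 97% |

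If 10% is instead the risk per 58 days of window, the row is 10%, 34% and 55%.

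**3. Two mixed cohorts of 6, *p* = 10% in both** (illustrative courses received).
- Cohort S, courses 1, 1, 1, 2, 2, 2: (3 × 0.100 + 3 × 0.190)/6 = 14.5%
- Cohort L, courses 1, 2, 5, 5, 10, 10: (0.100 + 0.190 + 2 × 0.410 + 2 × 0.651)/6 = 40.2%

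The ratio is 40.2/14.5 = 2.8. Cohort L shows more patients with an event with probability 0.78 and fewer with probability 0.07. At *p* = 5% the two figures are 7.4% and 23.4%; at 20% they are 28.0% and 61.5%.

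**4. The direction can reverse.** Suppose cohort S is the higher dose, with short exposure because of toxicity, and its per-course risk is double (20% against 10%). The tables would show 28.0% at the higher dose and 40.2% at the lower, hiding a real dose effect.

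**5. Front-loaded risk.** Assume 20% in course 1 and 2% in each later course. Incidence is 20% after 1 course, 1 − 0.8 × 0.98^4 = 26% after 5, and 1 − 0.8 × 0.98^9 = 33% after 10. With 1 − 0.8 × 0.98 = 21.6% after 2 courses, cohorts S and L would show (3 × 0.200 + 3 × 0.216)/6 = 20.8% and (0.200 + 0.216 + 2 × 0.262 + 2 × 0.333)/6 = 26.8%. The distortion remains but is much smaller.

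**6. Course 1 only.** Under the assumption in step 2, a Course 1 table has expectation *p* in every column. The footnote 1 window is close to equal but not identical: 42 days for a patient who starts cycle 2 on schedule, and 28 + 30 = 58 days for one who stops after a full course.

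**The case against.** - **The tables are descriptive.** No formal tests are planned, and the MTD rests on first-course DLTs in the MTD evaluation set. This stands: a reader might infer that MTD determination is compromised, and it is not. It does not cover the events that inform the recommended dose without being DLTs.
- **Later-cycle events are meant to count.** Protocol 3.1.1 has the safety committee consider repeated cycles, and protocol 5.2.1 brings DLT-type events after cycle 1 into the choice of recommended dose. This stands, and it rules out replacing the all-course tables with Course 1 tables.
- **Exposure is reported by dose in SAP 7.7.** With few patients per cohort a reader can set it beside the AE tables. That helps, but it does not show in which course events occurred.
- **The time course may be covered elsewhere.** SAP 7.8.1 refers to internal AE standards that are not provided, and SAP section 4 on changes to the planned analysis has no text in the version available. A reader might infer that the protocol's measure was deliberately dropped. The documents do not show that, and the maximum-grade half of the measure is kept. What can be said is that the time course is not listed.
- **Exposure need not rise with dose.** The statement about no expected activity covers only the four single-patient cohorts. Protocol 4.1.4.3 ties DLTs and severe infusion or cytokine reactions to stopping treatment, although it also mentions continuing at a lower dose. A one-directional bias is therefore not supported.
- **The quoted counting rule concerns subjects against events, not the window.** Correct. By-course subject counts would comply with it, so the remedy needs no change to that rule.

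**Conclusion.** The point holds as a confounding of dose with time on drug in every AE category except the Course 1 DLT table, together with a protocol-named key measure that the SAP as provided does not list. It should be corrected, because the planned tables would give incidences by dose over unequal windows for events that bear on the recommended dose.

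The size is illustrative only, since no AE rate is given. At an assumed constant 10% per course, incidence moves from 10% to 41% to 65% over 1, 5 and 10 courses, and the mixed cohorts differ about 2.8-fold with no dose effect. A reader might take from the table of risks that a 4- to 8-fold spurious effect is to be expected (41/10 = 4.1; 40/5 = 8). That would require every patient in one group to have one course and every patient in the other to have 5 or 10, with a low and constant risk. With risk concentrated in course 1, the largest ratio in the example is 33/20, about 1.7. The direction of the bias cannot be stated in advance.

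**What to change.** In SAP 7.8.1, keep the all-course tables and add, by dose group:

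1. Course 1 tables for all AEs, drug-related AEs, grade 3 or higher AEs, SAEs and AESIs, using the window already defined in footnote 1.
2. A table by course (1, 2, 3+) of maximum CTCAE grade with the number of patients at risk in each course. This supplies the time course named in protocol 7.3.4.

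Pool the four lowest doses in these displays, as SAP 6.1 already allows. State that the Course 1 tables are read alongside the all-course tables when doses are compared, not in place of them.

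The cost is a few more tables from data already collected. Cells will be small in later courses, and the patients still at risk there are a selected group, so the by-course table should be read as description.

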3. INTRODUCTION

As per ICH E9 [1], the purpose of this document is to provide a more technical and detailed elaboration of the principal features of the analysis described in the protocol, and to include detailed procedures for executing the statistical analysis of the primary and secondary variables and other data.

This TSAP assumes familiarity with the Clinical Trial Protocol (CTP), including Protocol Amendments. In particular, the TSAP is based on the planned analysis specification as written in CTP Section 7 “Statistical Methods and Determination of Sample Size”. Therefore, TSAP readers may consult the CTP for more background information on the study, e.g., on study objectives, study design and population, treatments, definition of measurements and variables, planning of sample size, randomization.

SAS[®] Version 9.4 or newer version will be used for all analyses.

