Table 6.1: 2 Definition of treatment periods

Analyzing Treatment Period	Start Date	Start Time	End Date
Screening	Date of informed consent		Date of the first administration of BI 836909
Treatment	Date of the first administration of BI 836909	Time of the first administration of BI 836909	Date of the last administration of BI 836909
Residual effect period	Date of the last administration of BI 836909 + 1 day		Date of the last administration of BI 836909 + 30 day
Post-treatment	Date of the last administration of BI 836909 + 31 day		Not applicable

For safety analyses, adverse events (AEs) will be classified to one of the following time periods: “Screening”, “Treatment”, or “Post-treatment”. Section 5.2.2 of the protocol specifies that all AE reported within 30 days of the last trial medication will be considered on treatment. Detailed rule for assigning AEs to these time periods are listed below:

- If the date of informed consent \leq AE onset date $<$ date of first administration of BI 836909, then the AE is assigned to “Screening”;
- If date of first administration of BI 836909 \leq AE onset date \leq date of last administration of BI 836909 + 30 days, then the AE is assigned to “Treatment”;
- If AE onset date $>$ date of last administration of BI 836909 + 30 days, then the AE is assigned to “Post-treatment”.

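### The SAP assigns adverse events by onset date alone and omits the protocol's rule that a pre-dose event which worsens on drug is treatment-emergent

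*SAP*

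**What the plan says.** **Protocol 7.3.4 (Safety analyses)** defines treatment-emergent events in two parts. The first is a time window: "all adverse events occurring between start of treatment and end of the residual effect period". The second is an extension: "Adverse events that start before first drug intake and deteriorate under treatment will also be considered as" treatment-emergent.

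**SAP 6.1 (Treatments)** sets the rule that will be programmed: "For safety analyses, adverse events (AEs) will be classified to one of the following time periods", namely screening, treatment or post-treatment. The test is the onset date. If onset falls on or after consent but before the "date of first administration of BI 836909, then the AE is assigned to" screening. Onset from first dose to last dose + 30 days goes to treatment, and later onset goes to post-treatment.

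**SAP 7.8.1 (Adverse events)** says "The analysis of adverse events will be based on the concept of treatment emergent adverse events", then restates the allocation: "All adverse events occurring before first drug intake will be assigned to" screening. Neither SAP section mentions worsening.

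**SAP 3 (Introduction)** says that "the TSAP is based on the planned analysis specification as written in CTP Section 7", which is the part of the protocol that holds the deterioration clause.

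**The concern.** The SAP presents its AE analysis as a treatment-emergent analysis built on protocol Section 7, but it implements only the first half of the protocol's definition. An event that is mild in screening and severe on drug is the kind of event the second half exists to catch.

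Such events can be in the database. Protocol 5.2.3 collects AEs from the signing of consent, and the screening period runs from Day -21 to Day -1.

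Safety is part of the primary objective, and the period assignment decides which events enter the AE tables. An event placed in screening by its onset date would be missing from the tables of all AEs, grade 3 or higher AEs, serious AEs and drug-related AEs. The direction is one-sided, because leaving events out can only lower the on-treatment counts.

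**Working it through.** The plan states no figure here and no formula applies. The check applies both rules to the same event.

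**Inputs**

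1. Protocol 7.3.4: window from start of treatment to the end of the residual effect period, plus events with earlier onset that deteriorate under treatment.
2. SAP 6.1 and 7.8.1: allocation by onset date, with no worsening clause.
3. SAP 7.8.1, collapsing rule: several occurrences on the case report form become one AE only if every listed attribute is the same, intensity included, and the occurrences overlap or adjoin in time.
4. Protocol 5.2.3: AEs are recorded from consent. The information named for each AE includes onset, end date and intensity, given as examples. A date of worsening is not named.

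**Hypothetical event:** grade 1 from Day -5, grade 3 from Day 10.

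| How the site enters it | Protocol 7.3.4 | SAP 6.1 and 7.8.1 |
|---|---|---|
| One record, onset Day -5, highest grade 3 | Treatment-emergent (deteriorated under treatment) | Screening (onset before first dose) |
| Two occurrences: grade 1 from Day -5, grade 3 from Day 10 | Treatment-emergent | Grade 1 part to screening, grade 3 part to treatment. They are not collapsed, because intensity differs |

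In the first row the documents give opposite answers. In the second they agree that the grade 3 event belongs to treatment. Whether the SAP loses the event therefore depends on data entry.

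**Do the documents settle the data-entry question?** No. Protocol 5.2.3 does ask for worsening of pre-existing conditions to be recorded, and it treats abnormalities present before trial inclusion as baseline conditions. It does not say that an AE arising between consent and first dose gets a new record when it worsens. The collapsing rule shows that the SAP expects some AEs to arrive as several occurrences. It does not require that for a change in grade.

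**Course 1 DLT table.** SAP 7.8.1 defines Course 1 as a window that opens at start of treatment. It does not say which date of an event is compared with that window: the first onset, or the date on which the event became dose-limiting.

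**The case against.** The best counter-argument is the SAP's own collapsing rule. Occurrences that differ in intensity, seriousness or relationship stay separate, so a worsening entered as its own occurrence already counts under treatment. This stands, and it limits the practical loss. It does not remove the conflict, because nothing in the documents obliges sites to enter a worsening that way.

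Three further points also stand in part:

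- Laboratory worsening has separate cover. SAP 7.8.2 tabulates grade transitions from baseline and flags increases of at least one grade to grade 2 or higher, whatever the AE onset.
- AE tables count patients, not events. A patient with any other on-treatment AE still appears in the overall incidence, so a loss would show mainly in specific terms and in the severity, seriousness and relatedness tables.
- SAP 7.8.1 defers details to sponsor standards that are not available here, and the available text of SAP Section 4 (changes in the planned analysis) is only a heading. It cannot be claimed that the narrower rule was undeclared, nor that the standards restore the clause.

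A reader might also infer that a lost DLT could turn 2 of 6 patients into 1 of 6 and so change the MTD. The documents do not support that. Under protocol 3.1.1 the safety committee decides on all available clinical and safety data. A DLT must be drug-related (protocol 5.2.1.1), and it is an adverse event of special interest that is reported to the sponsor within 24 hours (protocol 5.2.2.1 and 5.2.3). The SAP does not say that DLTs are filtered by the onset of an earlier, milder record.

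**Conclusion.** The written conflict is certain. Protocol 7.3.4 counts a pre-dose AE that deteriorates under treatment, and SAP 6.1 and 7.8.1 as worded do not. The consequence is conditional: it arises only for a screening-onset AE that worsens on drug and is held as a single record. In that case the event is missing from the treatment-emergent tables, and the bias is towards a cleaner profile.

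The size cannot be computed. The documents give no number of screening-onset AEs and no data-entry rule, so the effect may be small or nil. It is tempting to express one patient as a percentage of a cohort of 1, 3 or 6, but that range would mislead. Up to 6 more patients may be treated at the MTD or recommended dose, the lowest four doses are pooled for the DLT display (SAP 7.4), and the number of affected patients is unknown. The finding concerns the reported safety tables. It is not evidence that dose escalation or the MTD would change.

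**What to change.** 1. In SAP 6.1 and 7.8.1, add the protocol's clause: an AE with onset before first dose that worsens between first dose and last dose + 30 days is assigned to the treatment period, using the date of worsening where it is recorded.
2. Alternatively, require in the data-entry instructions that each worsening after first dose is entered as a new occurrence with its own onset date. The existing SAP rule then gives the protocol's answer.
3. State that the Course 1 DLT table uses the date on which the event met the DLT definition.
4. If the narrower definition is intended, declare and justify it in SAP Section 4.

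**Cost.** Where worsening is dated or entered separately, this takes a sentence in each of two SAP sections, one on the DLT table, and little or no programming. Where it is not, sites would have to supply the dates for the affected records. A listing of AEs with onset before first dose that were still ongoing at first dose would show how many records that involves.
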